## **5.5. Data Storage and Security**

Any datasets and computer files are referred to by study ID. The study ID is also used on all analytical files. The Penn Medicine Academic Computing Services (PMACS) will store all data securely sent to the Penn research team. The data center is housed in Information Systems and Computing at [name]. All data are stored in a single relational database, allowing researchers to correct mistakes. The same unique study ID is used to link these outside data to the participants. All data for this project will be stored on the secure/firewalled servers of the PMACS Data Center, in data files that will be protected by multiple password layers. These data servers are maintained in a guarded facility behind several locked doors, with very limited physical access rights. They are also cyber-protected by extensive firewalls and multiple layers of communication encryption. Electronic access rights are carefully controlled by UPenn system managers. This multi-layer system of data security, identical to the system protecting the University of Pennsylvania Health Systems medical records, greatly minimizes the risk of loss of privacy.

# **6. HUMAN SUBJECTS**

## **6.1. Risks to Human Subjects**

This project proposes minimal risk. There is a risk of breach of confidentiality for participants receiving study information from TrueMotion. For the Penn research team project is primarily a data assessment of an existing dataset, and all information used was gathered previously by Progressive and TrueMotion and is de-identified.

## **6.2. Adequacy of Protection Against Risk**

Participants are Progressive Insurance Snapshot® customers that have the Snapshot® app downloaded onto their mobile devices. Customers have agreed to have data sharing and location services turned on. These users have previously agreed to Snapshot® terms of service (<https://www.progressive.com/support/legal/snapshot-app-terms-conditions/?theme=neutral>) and privacy statement (<https://www.progressive.com/support/legal/snapshot-privacy-statement/>). Progressive will assign a Research ID to each Study Participant. Progressive and TrueMotion will not disclose to the

University the key for the association of Study Participant to Research ID. Data will be transferred between research partners using encryption and password protection, as described in section 5.4.

The University of Pennsylvania research team will not have access or hold any PHI for any of these users. All user names have been de-identified. Prior to sharing the data with us TrueMotion will remove identifiers (email address).

### **6.2.1. Recruitment and Informed Consent**

Progressive will designate a cohort of customers to invite to study on Day 30 to 70 of their Snapshot Mobile enrollment. This will be the “Eligible Cohort.”

Progressive will send an email to a subset of its customers who use the App with an invitation to participate in the Research by providing their express consent after the baseline period. The email will contain a link to a TrueMotion landing page specific to the Research and will contain a GUID. Once such a Progressive customer consents to participate, that customer will be considered a Study Participant for purposes of this study, until such time as a Study Participant elects to opt-out of participation. Progressive will assign the Study ID to each Study Participant. TrueMotion will provide Progressive with the GUID for each Study Participant and Progressive will then provide to TrueMotion the Study ID associated with such GUID.

Those interested will follow a link that takes them to a website hosted by TrueMotion with information about participating in the study. Those that wish to participate will opt-in to enroll online through the website hosted by TrueMotion.

### **6.2.2. Protection against Risk**

In order to protect study participants from potential risks related to the loss of confidentiality and due to any discomfort that they may experience in answering any questions, the following steps will be taken: 1) Participants will be told that they can withdraw from the study at any time by contacting us. 2) All information provided by the participant will be referenced to a subject ID#. The participant's ID# can only be connected to their identifiable information only through GUID mapping file held only by Progressive. The Penn research team will have no access to PHI. All data and files will be entered on computers protected by passwords and stored in a locked office. 3) All research staff will be trained in the importance of maintaining confidentiality and will undergo annual mandatory training of human subjects' research. 4) All participant data will be presented in aggregate and no individuals will be identified individually.

### **6.2.3. Potential Benefits to Individual Participants**

This information could allow the research team and Progressive to gain insight about effective usage based insurance (UBI) program strategies for reducing distraction from phone use while driving.

## **7. MONITORING**

### **7.1. Institutional Review Board (IRB)**

This study has been approved as an IRB exempt protocol.

### **7.2. Data Safety and Monitoring**

The limited data collected by TrueMotion through the Snapshot app and will be de-identified and manually uploaded by members of the TrueMotion team through secure .CSV files. Data will not be analyzed in real time. It will be securely stored on the study investigator's computers on a Penn Medicine secure network server using password protection and encryption. All data received will be de-identified and will remain de-identified. All data obtained in the study will be used exclusively for the purposes of the proposed research.

Users of this platform have been assigned a Study ID# and no identifiers will be contained in this file. This data will be linked by a programmer utilizing coded study IDs and operating behind a University firewall. The dataset is blinded of all personally identifiable information. (Variables in Appendix)

## **8. TIMELINE AND ENROLLMENT**

### **8.1. Timeline**

Study period is approximately 150 days.

- Phase 1: Baseline - 30 to 70 days (usual care monitoring in Snapshot program)
- Phase 2: Intervention - 50 days – delivered to opt-in Participants
- Phase 3: Post-intervention - remaining time until Snapshot rating complete (~30-60 days).

### **8.2. Screening and Enrollment**

Progressive will designate a cohort of customers to invite to study on Day 30-70 of their Snapshot Mobile enrollment. This will be the “Eligible Cohort.”

Progressive Snapshot users will be sent an email from Progressive about participating in research between day 30-70 of baseline. Those interested will follow a link that takes them to a website hosted by TrueMotion with information about participating in the study. Those that wish to participate will opt-in to enroll online through the website hosted by TrueMotion.

Once the participant is randomized, they will receive an email about their arm assignment. The email will provide details about the study (i.e. “What do I need to do?” and “How will I get paid?”) and contact information for any questions.

Once all 3,000 participants have been enrolled, the intervention period will begin (up to 2 weeks after enrollment).

## **9. FUNDING**

Funding for the present trial is provided by FHWA. The funding agencies have no role in the design and conduct of the study, collection, management, analysis, and interpretation of the data, preparation, review, or approval of the manuscript, or the decision to submit the manuscript for publication.

## **10. PUBLICATIONS**

We plan to publish the findings in conference proceedings and/or peer-reviewed journals.

## **11. DATA SHARING**

The investigator has a collaborative research agreement between Progressive, TrueMotion, and recipient researchers (University of Pennsylvania research staff) before sharing a limited dataset (driving trip summaries, phone usage, rating, etc.).

## **12. TASKS AND RESPONSIBILITIES**

Principal investigator: Overall responsibility for protocol development, intervention development, budget overview, data dictionary development, ethical approval, trial registration, trial oversight, and the data and safety monitoring board, assessment of overall recruitments, potential, data analysis, and dissemination and presentation of results.

Co-Investigators: Also protocol development, data dictionary development, trial oversight, dissemination of results.

## B. Final Statistical Analysis Plan

### 1. STATISTICAL ANALYSIS PLAN

#### 1.1. Analytic Methods

The primary outcome is **seconds of active handheld phone use per hour of driving**, which can also be expressed as active phone use %. We will use fractional regression with a logit link function as our primary analytic model to assess effectiveness between and among the 5 interventions. Specifically, we will evaluate these 10 predefined contrasts:

1. Social Comparison Feedback versus Control (monitor only)
2. End of Rating Period Incentive versus Control (monitor only)
3. End of Rating period Incentive + Social Comparison Feedback versus Control (monitor only)
4. Weekly Loss-Framed Incentive + Social Comparison Feedback versus Control (monitor only)
5. Larger Weekly Loss-Framed Incentive + Social Comparison Feedback versus Control (monitor only)
6. End of Rating Period Incentive versus Social Comparison Feedback
7. End of Rating Period Incentive + Social Comparison Feedback versus Social Comparison Feedback
8. End of Rating Period Incentive + Social Comparison Feedback versus End of Rating Period Incentive
9. Weekly Loss-Framed Incentive + Social Comparison Feedback versus End of Rating Period Incentive + Social Comparison Feedback
10. Larger Weekly Loss-Framed Incentive + Social Comparison Feedback versus Weekly Loss-Framed Incentive + Social Comparison Feedback

Although longitudinal models such as generalized estimating equations might be considered in light of the repeated trip measures among individual participants, fractional regression with a logit link is preferred in this case because the primary outcome collapses to a proportion between 0 and 1 that is weighted by travel time within and across trips. Furthermore, weekly feedback messages and incentives are delivered based on the weekly averages of seconds of active handheld phone use time divided by weekly total trip time. The model will be adjusted for: 1) length of time in the Snapshot program during the Baseline period; 2) and observed primary outcome during the Baseline period. Other covariates to be included in the model include:

1. Proposed baseline covariates to be included in primary outcome analysis model
2. Baseline period active phone use % (i.e. total active handheld phone use seconds / total trip seconds)
3. Proportion of period active phone use % due to handheld calls vs. handheld non-call use
4. Mean hours of driving/week during baseline period
5. Age
6. Sex
7. Marital status
8. Urban-suburban-rural residence
9. Residence in state with universal handheld ban
10. Race/ethnicity
11. Income
12. Education level
13. Phone type (iPhone vs. Android)
14. Baseline use of automated Do Not Disturb While Driving setting (Y/N)
15. Bluetooth/USB car connectivity (Y/N)
16. Dashboard touchscreen (Y/N)

17. Frequency of letting passenger use phone
18. Frequency of riding as a passenger
19. Number of prior traffic violations in prior 5 years
20. Number of car crashes in prior 5 years

Due to the multiple pre-planned contrasts, we will adjust for multiple comparisons using the Holm method. First, the 10 contrasts will be ranked (lowest to highest) based on the raw p-value from the logistic regression. For a contrast to be significant using the Holm threshold, the raw p-value must be below the threshold for each row calculated as  $(0.05 / [n \text{ remaining contrasts}])$ .

Correspondingly, for clarity of presentation, adjusted p values will be reported by multiplying the raw p value by the number of remaining contrasts. For example, the smallest p-value is multiplied by 10 to obtain the adjusted p-value.

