## **C. Summary of Changes**

### **Appendices:**

I: Trial Variable Table

II: Intake Survey

III: Exit Survey

TRIAL OVERVIEW Title	Comparative Effectiveness of Financial Incentives and Nudges to Reduce Cellphone Use While Driving Among UBI Auto Policy Holders (PUT-IT-DOWN Study)
Clinical Trials Number	NCT03833219
Sources of monetary or material support	FHWA
Study Sites	National cohort of Progressive Snapshot Mobile auto insurance policy holders
Conditions studied	Distracted driving
Interventions	Push notification reminders, social comparison feedback, and financial incentives
Comparator	Self-monitoring (control)
Inclusion criteria	
Progressive Snapshot Users with policy activated within recruitment period
 
Progressive Snapshot policy holder in one of the following states and regions: MI, PA, TX, FL, TN, OR, GA, NE, OK, OH, MT, MO, NV, CT, WI, MD, KY, MN, NH, NJ, AZ, ME, LA, SC, CO, MS, IN, IA, AL, ND, UT, RI, WV, WY, IL, AR, DE, KS, SD, NM, VT, ID, and the District of Columbia
 
Has an email address

Exclusion criteria	
 
1. Progressive Snapshot Mobile App not updated to enable push notifications
 
2. Customer's residential address is in a state in which phone use while driving is factored into insurance rating
 
3. Customer's Snapshot Mobile App does not collect trip data with all sensors active
 
4. Customer in Snapshot program for < 30 days or more > 70 days
 

Study type	
Interventional
 
Phase 1: Baseline – 30-70 days (usual care monitoring in Snapshot program)
 
 
• Phase 2: Intervention - 50 days – delivered to customers who agree to participate
 
• Phase 3: Post-intervention - remaining time until Snapshot rating complete (~30-60 days).
 

Randomization Arms	
 
1. Control (monitor only)
 
2. Social comparison feedback
 
3. End of rating period incentive
 
4. End of rating period incentive + social comparison feedback
 
5. Weekly loss-framed incentive + social comparison feedback
 

6. Larger weekly loss-framed incentive + social comparison feedback

Target sample size	3000 Participants 500 participants per study arm.

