## **2.10. Behavioral Interventions**

### **2.10.1. Intervention Arms**

Intervention Arm	Notifications	Incentive	
		Timing	Size
Driver Mode Nudge (all arms, iPhone users only)	3 times over 3 weeks: Prompt to enable Do Not Disturb While Driving. Linked to website with instructions and frequently asked questions: www.besafir.org/do-not-disturb .  Sample messages: Arms 1-2: "Reduce annoying notifications when driving (while keeping the urgent ones!). Enable Do Not Disturb While Driving. Tap here to learn how!"  Arms 3-6: "Increase your chance to earn \$ and reduce annoying notifications when driving (while keeping the urgent ones!). Enable Do Not Disturb While Driving. Tap here to learn how!"	N/A	N/A
1. Control (monitor only)	Continue in monitoring only mode	N/A	N/A
2. Social comparison feedback	Initial push notification: Told they will be compared to drivers like them each week and that they will receive up to 3 stars.	N/A	N/A

	
Weekly push notification:
 
a. Compare phone use % relative to Progressive Snapshot customers like them based (age, sex, marital status, urban/suburban/rural residence). Told can receive up to three stars.
 
 
• 1 star (if <50th percentile)
 
• 2 stars (if <math>\geq</math> 50th percentile, <90th percentile)
 
• 3 stars if <math>\geq</math> 90th percentile (top performer)
 
 
Sample message: “★ ★ out of 3 stars. Almost there! You're better than at least half of our drivers at staying off your phone. A little less swiping, typing, and holding the phone and you'll be one of our best drivers! ”
		
3. End of rating period incentive	
Initial notification:
 
a. Financial Incentive: Tell them they have a chance to win \$50 in 50 days for keeping handheld phone use to a minimum.
 
 
• If <50th percentile), then paid \$0
 
• If <math>\geq</math> 50th percentile, <90th percentile), then paid \$25
 
• If <math>\geq</math> 90th percentile (top performer), then paid \$50
 
	Redeemed at end of rating period	Max: \$50 (\$1/day)

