## 2.11. Assessment Controls

Participants allocated to the control arm that have iPhones will receive push notifications prompting them to enable Do Not Disturb While Driving once a week for 3 weeks, without receiving any feedback or goal support for the intervention period, 50 days.

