## 1.2. Sample Size, Power, and Minimum Detectable Differences

To have power of 0.80 to detect a clinically meaningful reduction of a 2% difference in amount of trip time spent actively using a phone (72 seconds/hour of driving), the minimum sample size is 1,842 (301 per arm).

With a target sample size of 3,000 and power of 0.80, we should be able to detect a difference between treatment arms of 52 seconds/hour of driving (i.e. an absolute reduction in phone use % of 1.44%). We would have a power of 0.94 to detect a difference of 60 seconds/hour of driving.

Proposed variables to be considered as effect modifiers in the primary analysis
1. iPhone vs. Android. Hypothesis: the relative reductions in active handheld phone use will be greater among those with iPhones due to the notification to encourage Do Not Disturb While Driving.
2. Quartile of baseline period active phone use % (i.e. total active handheld phone use seconds / total trip seconds). Hypothesis: the relative reductions in active hand held phone use while be greater among those in the highest quartile of baseline phone use due to greatest opportunity for improvement and least opportunity for improvement in the lowest quartiles.
3. Proportion of period active phone use % due to handheld calls vs. handheld non-call use. Hypothesis: the relative reductions in active hand held phone use while be greater among those with a greater proportion of handheld phone use due handheld call use vs. non-call use due to multiple available technological means to switch to handsfree calls.
4. Proposed variables to be considered as effect modifiers in hypothesis generating secondary analyses
5. Baseline use of automated Do Not Disturb While Driving setting (Y/N)
6. Baseline use of a phone mount
7. Mean hours of driving/week during baseline period
8. Age
9. Sex
10. Marital status
11. Urban-suburban-rural residence
12. Residence in state with universal handheld ban
13. Income
14. Education level

15. Number of prior traffic violations in prior 5 years
16. Number of car crashes in prior 5 years
17. Self-reported frequency of types of handheld phone use while driving (e.g. phone call, text messaging, adjusting navigation app, changing music app, social media app)
18. Willingness to give up phone use while driving scale
19. Automaticity scale of phone use while driving
20. Compulsive phone use scale
21. Delay discounting rate

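### SAP contrasts 1–5 are labelled against a monitor-only control, but control-arm iPhone users also receive three Do Not Disturb While Driving prompts, and the phone-type interaction cannot measure what those prompts do

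*Combined protocol and SAP*

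**What the plan says.** Final SAP section 1.1 lists ten contrasts. The first is "Social Comparison Feedback versus Control (monitor only", and contrasts 2–5 carry the same control label. The Comparator row of the Trial Overview reads "Self-monitoring (control", and the arm table in protocol 2.10.1 describes Arm 1 as "Continue in monitoring only mode".

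Directly above Arm 1 in that table is a row headed "Driver Mode Nudge (all arms, iPhone users only". Its content is "3 times over 3 weeks: Prompt to enable Do Not Disturb While Driving", with a link to a website giving instructions. Section 2.9 repeats that iPhone users in all arms are prompted. Section 2.11 is explicit about the control arm: "Participants allocated to the control arm that have iPhones will receive push notifications prompting them to enable Do Not Disturb While Driving once a week". SAP 1.3 confirms that Android users get no such prompts. The sample prompt for Arms 3–6 opens with a cue about earning money; the sample for Arms 1–2 does not.

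Protocol 3.1.3 defines the incremental cost-effectiveness ratio against the control arm and between intervention arms, without calling the control monitor-only.

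SAP 1.2 gives as its first effect-modifier hypothesis that "the relative reductions in active handheld phone use will be greater among those with iPhones due to the notification to encourage Do Not Disturb While" (the quotation stops inside the setting's name). SAP 1.3 says that assessing iPhone versus Android modification of the ten contrasts will allow the effectiveness of the prompts to be estimated.

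**The concern.** The label and the content of Arm 1 disagree. It is monitoring alone for Android users, and monitoring plus a prompt to change phone settings for iPhone users. The plan itself treats the prompt as active. The Trial Overview lists push reminders among the interventions, SAP 1.2 expects the prompt to reduce handheld use, and SAP 1.3 plans a mediation analysis through activation of the setting.

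Two wrong conclusions could follow. A null result in contrasts 1–5 could be reported as no better than monitoring, when for iPhone users it shows only no better than monitoring plus the prompt. And an iPhone–Android difference in those contrasts could be reported as the effect of the prompt, which the design does not isolate.

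**Working it through.** No figure in the plan has to be reproduced; this is a check of labels against content.

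**1. Prompt count in the control arm.** Section 2.11 has "prompting them to enable Do Not Disturb While Driving once a week for 3 weeks": 1 per week × 3 weeks = 3 prompts. This agrees with the three prompts in the arm table.

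**2. What each group receives.**

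| Phone | Arm 1 | Arm 2 | Arms 3–6 |
|---|---|---|---|
| iPhone | monitoring + prompt | monitoring + intervention + prompt | monitoring + intervention + prompt with earnings cue |
| Android | monitoring | monitoring + intervention | monitoring + intervention |

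No iPhone cell contains monitoring alone.

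**3. What contrasts 1–5 estimate.** On the seconds-per-hour scale, for iPhone users, let
- m = mean use under monitoring alone;
- d = reduction from the prompt;
- x = reduction from the intervention;
- i = any extra reduction (negative if they overlap) when both are given;
- w = any extra reduction from the earnings wording (0 in contrast 1).

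Control mean: m − d. 
Intervention-arm mean: m − d − x − i − w. 
Contrast, as a reduction: x + i + w.

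For Android users the contrast is x_A, a true comparison with monitoring alone.

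**4. Comparison with monitoring alone in iPhone users.**
- Intervention by itself: x. The contrast equals this if i = 0 and w = 0, whatever d is.
- Intervention plus prompt as delivered: x + d + i + w. The contrast falls short of this by exactly d.

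With iPhone share p, the pooled contrast falls short of the delivered package's effect over monitoring alone by p × d. The documents give neither p nor d. As an illustration only, assume p = 0.4 to 0.6 and d = 10 to 30 s/h. The gap then runs from 0.4 × 10 = 4 s/h to 0.6 × 30 = 18 s/h; with d = 0 it is zero. This is a gap between two different quantities, not a bias in the contrast.

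**5. What the phone-type interaction estimates.** iPhone contrast minus Android contrast = (x + i + w) − x_A. The term d has cancelled. What remains is a difference in response between two groups that were not randomised, plus any interaction and wording effect. A larger reduction in iPhone users may well appear, but it would not measure how effective the prompt is.

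**6. Precision of Android-only estimates.** If variance per person is the same for both phone types, the standard error is multiplied by about 1/√(1 − p): 1/√0.6 = 1.29 at p = 0.4, and 1/√0.4 = 1.58 at p = 0.6 (p again assumed).

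**The case against.** The strongest reply is that nothing is hidden. Sections 2.9, 2.10.1 and 2.11 state the prompt openly, and monitor-only is the short name of a fully described arm. A background co-intervention given in every arm is a legitimate choice. Phone type is a model covariate, its interaction is planned for all ten contrasts, and mediation through the setting is planned. The earnings cue, or greater uptake when money is at stake, could also produce larger iPhone contrasts despite a prompted control.

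Most of this stands. The design is sound and the prompt is disclosed. But adjusting for phone type does not change the comparator, and testing an interaction does not commit the team to reporting Android-specific estimates. Mediation analysis based on survey-reported activation does not create an unprompted iPhone group. The earnings cue explains how the SAP 1.2 hypothesis could come true, but the result would then reflect wording or interaction, not the prompt's own effect.

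Three stronger readings are tempting and are not supported:
- *That the trial can conclude nothing about iPhone users against monitoring alone.* The contrasts are internally valid over the prompted background. Step 4 shows that they speak to monitoring alone if effects add and the wording difference is inert.
- *That the prompted control leaves the trial underpowered.* SAP 1.2 defines its 52 s/h as a difference between arms, that is, arms as delivered. It is nowhere tied to an unprompted control. Any claimed loss would rest on an iPhone share and a prompt effect that the documents do not give, and the wording difference makes even its direction uncertain.
- *That the cost-effectiveness definition carries the wrong label.* Section 3.1.3 refers only to the control arm; it inherits the comparator.

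**Conclusion.** The point holds as a fault of labelling and interpretation, not as a bias in the randomised contrasts. Five of the ten confirmatory contrasts name a comparator that no iPhone user was assigned, and cost-effectiveness ratios against control share that comparator. For iPhone users, contrasts 1–5 estimate the effect added to monitoring plus the prompt; contrasts 2–5 also include the difference in prompt wording, as far as the sample messages represent what was sent. Separately, the phone-type interaction does not estimate the prompt's effectiveness, contrary to SAP 1.2 and 1.3. These conclusions follow from the text and need no assumed figure. The numerical size in the pooled sample cannot be determined from the documents. The plan should be corrected because, followed as written, it invites two wrong statements in the report and the correction is nearly free.

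**What to change.** 1. In SAP 1.1 (contrasts 1–5) and the Trial Overview, restate the comparator as *monitoring, plus Do Not Disturb While Driving prompts in iPhone users*. Word conclusions, including those from the cost-effectiveness ratio against control, as effects over that background. Note that for iPhone users contrasts 2–5 include the prompt-wording difference.
2. Pre-specify that contrasts 1–5 are also reported within Android users, with confidence intervals, from the interaction model already planned in SAP 1.3. Describe them as supportive and as the only randomised estimates against monitoring alone.
3. In SAP 1.2 and 1.3, drop the statement that the phone-type interaction estimates the effect of the prompt. The interaction itself can stay as a description of whether effects differ by phone type.

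The 52 and 60 s/h statements in SAP 1.2 need no change on this account.

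The cost is wording plus one extra set of estimates from a planned model, with no new data. The Android estimates will be less precise than the pooled ones and do not carry over to iPhone users without assumptions. The headline claim becomes slightly narrower.
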